### SECTION 3: ANALYSIS PLAN

**3.1.1 Power analysis.** Sample size requirements were calculated taking into account a unique design effect for the SWD, such that  $N_{sw} = Nu \times DE_{sw}$  (where  $Nu$  is the total number of students needed to detect the treatment effect with a power of 80% and a significance level of 0.05, uncorrected for cluster and repeated measurements). The design effect was calculated as:

$$DE_{sw} = \frac{1 + \rho(ktn + bn - 1)}{1 + \rho\left(\frac{1}{2}ktn + bn - 1\right)} \times \frac{3(1 - \rho)}{2t(k - \frac{1}{k})}$$

where  $k$  is the number of steps,  $n$  is the expected number of students per cluster,  $b$  is the number of baseline measurements,  $t$  is the number of measurements after each step, and  $\rho$  is the intra-class correlation coefficient, estimated to be 0.016 based on findings reported by Kaufman et al. With an  $\rho$  of 0.05, power of 0.8,  $Nu = 292$ ,  $DE_{sw} = 1.3273$ , and the expectation of 15% attrition during the study, a sample size of 456 will allow the detection of a 0.14 increase in the proportion of condom use relative to the frequency of sexual intercourse from baseline to the 12-month observation period hypothesized under Aim 2.

**3.1.2 Missing data.** Attrition is likely to covary with truancy, suggesting a missing data mechanism that is not missing at random (NMAR). To address this, a dropout variable  $D_i$  will be developed for each individual across the 4 observation periods, where  $D_i=k$  for dropout between the  $(k-1)$  and  $k^{\text{th}}$  occasion. A model of the probability of dropout, where

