$\log \left\{ \frac{\Pr(D_i=k \mid D_i \geq k, Y_{i1}, \dots, Y_{ik})}{\Pr(D_i>k \mid D_i > k, Y_{i1}, \dots, Y_{ik})} \right\} = \theta_1 + \theta_2 Y_{ik-1} + \theta_3 Y_{ik}$  presumes that  $\theta_3 \neq 0$  for the NMAR mechanism. Missing data will be examined using multiple imputation, where missing values are replaced by a set of  $m$  plausible values using a propensity scoring sequence to generate a single estimate of the parameters of interest. Observations will first be grouped on the basis of propensity score similarity, then individuals with missing values will be randomly matched to those with observed values, and finally missing values will be randomly selected with replacement from the random sample of observed values. This sequence will be repeated sequentially starting at the 3-month follow-up observation through the 12-month follow-up observation, and the entire propensity scoring and time imputation sequence(s) will be repeated at minimum across 2:5 datasets ( $m$ ) to estimate  $\bar{\beta} = \frac{1}{m} \sum_{k=1}^m \hat{\beta}^{(k)}$ . Sensitivity analyses will also be used to assess the robustness of primary results attributable to missing data by examining imputed and nonimputed data.

**3.1.3 Dose.** The treatment dose is the number of intervention components delivered to the individual student, accounting for individual students' attendance and participation. This will be tracked using the fidelity log, staff field notes, and the CAB meeting. A count, nominal, or weighted percentage will be used to represent dose pending analysis of the dose frequency distribution.

**3.1.4 Baseline data analysis.** Baseline data will first be analyzed to determine whether demographic and SRH variables vary relative to school (cluster). The psychometric properties of scales will be explored, and confirmatory factor analyses (CFA) for scales will be conducted. Finally, structural equation models (SEM) will

Woertman W et al. Stepped wedge designs could reduce the required sample size in cluster randomized trials. *J Clin Epidemiol*. July 2013;66(7):752-758.

Kaufman C et al. Effectiveness of Circle of Life, an HIV-preventive intervention for American Indian middle school youths. *Am J Public Health*. June 2014; 104(6):e106-e112.

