**Table 2. NIE Measures.**

**Table 2. N/E Measures.**

Data Collection Instruments and Measures	Data Collection: Baseline & Months				Description of Measures Number of Items; Scale Anchors; Benchmark Values	
	Base	3	9	12		
Student Survey						
Primary Outcome Variable						
Proportion of condom use during sexual intercourse (SI)	X	X	X	X	2 items; number of times condom used relative to number of times had SI	
Secondary Outcome Variables						
Age of onset of sexual intercourse	X	X	X	X	2 items; ever had SI & age at first SI	
Number of sex partners	X	X	X	X	2 items; lifetime & past-month sex partners	
Frequency of sexual intercourse	X	X	X	X	1 item; frequency of SI in past month	
Pregnancy history	X	X	X	X	1 item; number of pregnancies	
Type & frequency of birth control (BC) during sexual intercourse	X	X	X	X	3 items; type of BC use and number of times BC used during SI	
Type & frequency of substance use (SU) during sexual intercourse	X	X	X	X	1 item measures SU with SI; 5 items measure lifetime and past month SU	
Tertiary Outcome Variables						
Type & frequency of parent/legal guardian-child SRH communication	X	X	X	X	24 items Likert scale; higher score = higher communication	
Cultural identity & participation in cultural activities	X	X	X	X	3 items cultural identity ( $\alpha = .75$ ); 2 items cultural activities engagement ( $\alpha = .46$ )	
Type & frequency of SRH services	X	X	X	X	9 items; frequency, type, and follow-up of SRH services used	
Other Variables						
Motivation to avoid STIs, HIV, HCV, & pregnancy	X	X	X	X	Up to 9 items; 1 (very true) to 5 (very untrue); 1 = more positive attitude/motivation	
Condom & birth control use intention & self-efficacy	X	X	X	X	4 items per intention; 1 (very true) to 5 (very untrue); 1 = higher intention; 6 self-efficacy items; 1 (very easy) to 4 (very hard); 1 = high self-efficacy	
Abstinence	X	X	X	X	3 items; 1 (strongly disagree) to 4 (strongly agree); 4 = more supportive of teen abstinence	
Refusal skills regarding sex	X	X	X	X	7 items; 1 (I definitely can say no) to 5 (I definitely can't); 1 = stronger refusal skills	
Knowledge of STIs, HIV, HCV, pregnancy, & health relationships	X	X	X	X	Range of 4 to 10 items per topic; True/False/DK; Average proportion of questions correct	
Depression (CES-D) & exposure to stressful life events	X	X	X	X	CES-D — 7 items ( $\alpha = .80$ ); Life Events — 24 items; Yes/No; number of events observed	
Student Demographics						

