H1: AI youth who participate in N/E will demonstrate increased condom use at 3, 9, and 12 months. (12 months will be used in the Primary Outcome analysis; 3 and 9 months will be used in the Secondary Outcomes analysis.) H2: AI youth who participate in N/E will demonstrate increased use of other birth control at 3, 9, and 12 months. They also will demonstrate a decrease in sexual risk behaviors as measured by reduced number of sex partners, delayed onset of sexual intercourse, and decreased substance use during sex, at 3, 9, and 12 months. (Secondary Outcomes) H3: N/E parents/legal guardians and youth will demonstrate significantly increased communication about topics related to SRH at 3, 9, and 12 months. AI youth who participate in the cultural mentoring program will demonstrate significantly increased understanding of cultural values related to traditional AI beliefs regarding SRH at 3, 9, and 12 months. And AI youth who participate in N/E will report significantly increased use of SRH services at 3, 9, and 12 months as a result of improved coordination among education, health care, and social service agencies on the Fort Peck Reservation. (Tertiary Outcomes) AIM 3: Evaluate the fidelity and acceptability of N/E. N/E's fidelity and acceptability will be evaluated using qualitative methods, including focus groups, activity logs, and staff field notes and meetings.

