5.1 Have you ever had sexual intercourse? Yes No

*If you have never had sexual intercourse, skip to Section 6.*

5.2 How old were you when you had sexual intercourse for the first time?

- a. I have never had sexual intercourse
- b. 11 years old or younger
- c. 12 years old
- d. 13 years old
- e. 14 years old
- f. 15 years old
- g. 16 years old
- h. 17 years old or older

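### The hot-deck imputation does not tie donors to the student's own last answer, so ever having had intercourse can be imputed backwards and onset overstated among students not yet active

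*Combined protocol and SAP*

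**What the plan says.** Section 3.1.2 (Missing data) expects attrition to go with truancy and treats it as not missing at random. It writes a dropout model with an intercept, the previous response and the current response. It then describes the imputation: observations are grouped by similarity of propensity score, "then individuals with missing values will be randomly matched to those with observed values, and finally missing values will be randomly selected with replacement" (donors being students with an observed answer), and this is repeated visit by visit from 3 to 12 months over several datasets. The section does not list the covariates in the score, does not say which outcome the response in the dropout model is, and gives no rule for outcomes that can only move one way. The comparison of imputed with nonimputed data is stated for primary results.

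The outcome most affected is onset. H2 in the registration record's Detailed Description includes "reduced number of sex partners, delayed onset of sexual intercourse". Table 2 measures onset at every visit by "2 items; ever had SI & age at first SI", and item 5.1 of the student survey asks "Have you ever had sexual intercourse". Lifetime sex partners and number of pregnancies are also secondary measures in Table 2. Section 3.1.5 on generalized linear mixed-effects models (GLMM) puts binary secondary outcomes into a GLMM and names no subset of students not yet active.

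**The concern.** Ever having had intercourse cannot go from Yes to No, and lifetime partners and pregnancies cannot fall. A student who answered Yes at baseline has a known 12-month answer, and no imputation is needed. A student who answered No should be imputed at the onset rate of students who were also No.

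The written donor rule guarantees neither. A propensity score for missingness balances who is missing. It does not preserve the link between a student's successive answers. If a propensity group mixes active and not-yet-active students, an active student can draw a No, and a not-yet-active student can draw a Yes from a donor who was active all along. Onset among students not yet active is then overstated, and the within-student histories passed to the GLMM contain impossible sequences. The planned sensitivity comparison does not commit the team to looking at H2.

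**Working it through.** **Inputs from the plan.** Section 3.1.1 gives 292 students before correction, a design effect of 1.3273 and "the expectation of 15% attrition during the study". These reproduce the sample size: 292 × 1.3273 = 387.57, and 387.57 / (1 − 0.15) = 455.97, so 456. I use N = 456 and take the 15% as the share missing at 12 months.

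**Assumed inputs, not in the documents.** Active at baseline p0 = 0.40 to 0.60; true 12-month onset among the rest h = 0.15 to 0.25. The second table below uses h of about 0.10.

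**Worst mixing: the draw is unrelated to the student's earlier answer.** With m = 0.15 and true 12-month prevalence p1 = p0 + (1 − p0)h:

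- apparent onset among baseline-inactive students = (1 − m)h + m·p1
- impossible Yes-to-No reversals = N·p0·m·(1 − p1)

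| p0 | h | p1 | Apparent onset | Ratio to true | Reversals in 456 |
|---|---|---|---|---|---|
| 0.40 | 0.15 | 0.49 | 0.201 | 1.34 | 14.0 |
| 0.40 | 0.25 | 0.55 | 0.295 | 1.18 | 12.3 |
| 0.50 | 0.15 | 0.575 | 0.214 | 1.43 | 14.5 |
| 0.50 | 0.20 | 0.60 | 0.260 | 1.30 | 13.7 |
| 0.60 | 0.15 | 0.66 | 0.227 | 1.51 | 14.0 |
| 0.60 | 0.25 | 0.70 | 0.318 | 1.27 | 12.3 |

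The p0 = 0.50, h = 0.20 row by hand: 0.15 × 456 = 68.4 missing, 34.2 in each group. Active: 34.2 × 0.40 = 13.7 imputed No. Inactive: 34.2 × 0.60 = 20.5 imputed Yes, against 34.2 × 0.20 = 6.8 expected. The excess onsets, 20.5 − 6.8 = 13.7, equal the reversals, so overall prevalence stays at p1.

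**What the score's content changes.** Simulated propensity-class hot deck: 456 students, 15% missing, p0 = 0.45, true onset about 0.10, up to five classes, 300 runs, one follow-up. Dropout coefficients are log-odds; a truancy-type covariate with coefficient 1 drives dropout in every row except the first.

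| Score contains | Imputed onset | Reversals among baseline-active | Prevalence, true → imputed |
|---|---|---|---|
| Prior answer only (0.7) | 0.100 | 0 | 0.506 → 0.507 |
| Prior answer (0.7) and truancy | 0.153 | 6.9% | 0.504 → 0.502 |
| Prior answer (1.5) and truancy | 0.132 | 4.7% | 0.506 → 0.503 |
| Prior answer (0, unrelated to dropout) and truancy | 0.161 | 7.2% | 0.505 → 0.506 |
| Truancy only, though prior answer predicts dropout (0.7) | 0.142 | 10.2% | 0.504 → 0.482 |

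The last row is 0.102 × 0.45 × 456 = about 21 reversals.

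**Wider grid.** With p0 0.40-0.60, h 0.15-0.25, an odds ratio of dropout for active students of 1 to 3, a truancy odds ratio of 2 per SD, and both in the score (quintiles, 400 runs per scenario), reversals were 6.2 to 14.5 per imputed dataset and the onset ratio 1.11 to 1.52. At p0 = 0.50, h = 0.15 and odds ratio 1, imputed onset was 0.214, against 0.149 in observed students alone. With donors restricted to the same prior status it was 0.150, with no reversals.

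With the prior answer alone in the score and h = 0.20, imputed onset was 0.196 to 0.201 with no reversals when groups followed the score values. Forcing that score into rank quintiles gave 0.199 to 0.214 and about 1 to 4 reversals.

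**The case against.** The strongest reply is that the only dropout model written in section 3.1.2 contains the previous response. The current response is unobserved for a dropout, so a score built on that model alone uses just the student's own prior answer. If that response is ever having had intercourse, the groups separate students by it and the problem disappears, as the simulation confirms. Truancy is named as going with attrition but is not a term in the model, and neither Table 2 nor the student survey has a truancy item; attendance is tracked for dose in section 3.1.3 but not linked to imputation. This stands, and it puts zero in the range. It does not settle the matter: the score's covariates are not listed, the response is not tied to a particular outcome, and a team that takes its own remark about truancy seriously would add such a covariate.

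A reader might go further than the documents allow in four ways.

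- That the imputation never uses the earlier answer. The score may carry it indirectly.
- That H2 as planned is biased. The plan does not define onset among baseline-inactive students as the quantity estimated. If the GLMM models ever-sex in all students, false onsets and reversals nearly cancel in the mean.
- That the excess can be judged against the 0.14 in section 3.1.1. That figure is a change in condom use and is no yardstick for onset.
- That the fault favours the intervention. Section 2.3.5 places follow-up surveys after a school has begun, so false onsets would fall in intervention time and count against N/E.

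The simulations cover ever-sex at one follow-up. They omit schools, calendar time, the sequential visits, lifetime partners and pregnancies, so I draw no conclusion about the precision of the GLMM effect.

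**Conclusion.** The concern holds as a gap in a stated method. Nothing in section 3.1.2 matches donors on the student's last answer or keeps one-way outcomes from reversing, so consistency depends on the propensity groups happening to separate students by that answer.

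For 456 students with 15% missing, under the assumed 40-60% active at baseline and 15-25% true onset, the effect runs from none to about 14 impossible reversals per imputed dataset and onset inflated by up to about 50% among baseline-inactive students. Which end applies depends on whether the score rests on the prior answer alone or also reflects truancy. Reversals can be higher, about 21 in the case shown at 10% onset, if the prior answer is left out of the score although it predicts dropout; overall prevalence is then biased too (0.482 against 0.504). With the prior answer in the score, prevalence is nearly unbiased.

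The harm is to onset among students not yet active and to within-student histories, on secondary outcomes. It is worth correcting because the remedy is cheap and removed both faults in simulation.

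**What to change.** In section 3.1.2:

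1. Carry forward a prior Yes on ever having had intercourse without a draw.
2. For lifetime partners and pregnancies, allow only donors whose value is not below the student's last value. State how a Not sure answer to survey item 5.11 is treated.
3. For each imputed outcome, form donor groups by last observed status of that outcome first and by propensity within that, merging neighbouring propensity groups where donors are few. Because imputation proceeds visit by visit, a value imputed at an earlier visit should bind later ones in the same dataset.
4. Analyse delayed onset among students not active at baseline, using this imputation. Say what that analysis compares, since the documented follow-up surveys come only after a school has begun.

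Listing the score's covariates in the same paragraph would remove the ambiguity that drives the range above. The cost is SAP wording and a few lines of code, with no new data. The downside is smaller donor pools, so fewer propensity groups may be workable at some visits.

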completed treatment. ***Following randomization of the schools to the intervention, there will be three waves of implementation: Wave 1 (1 school in 2019), Wave 2 (2 schools in 2019-2020), and Wave 3 (2 schools in 2020-2021).*** The 5 schools on the Fort Peck Reservation will be the clusters that are randomized to *NIE*. *NIE* will take approximately 40 weeks, or 3 quarters, to implement. The first observation period (Q4 of Year 2) provides baseline measurements for all respondents drawn from every cluster. The cluster is then surveyed at 3, 9, and 12 months for the students in the cluster once they have begun participation in the intervention, and at 9 and 12 months for the parents/legal guardians in the cluster once they have begun participation in the intervention. Following completion of the intervention across all clusters, we will conduct the quantitative analysis. The SWD allows us to control for the effect of time and ensure that the full AI population of schools at Fort Peck receives *NIE*. The systems-level component of *NIE* will be implemented reservation-wide rather than school-wide during Years 2 to 4 of *NIE* as the SWD is rolled out. The systems level component will be measured and analyzed qualitatively.

**2.3.6 Trial Timeline.** The timeline for *NIE* is: Year 1-Refine, tailor, and finalize the components of *NIE* with the CAB by reviewing our current quantitative and qualitative data from Fort Peck and by talking with elders

[figure not shown]

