$Y_{ijl} = \mu + \beta_j + \theta X_{ij} + u_i + e_{ijl}$ , and where  $u_i \sim N(0, \sigma_u^2)$ ;  $e_{ijl} \sim N(0, \sigma_e^2)$ , with  $\beta_j$ =the fixed effect of time,  $X_{ij}$ =intervention (0,1 or dose representation),  $\theta$  =intervention effect,  $u_i$ =random effect for cluster, and  $e_{ijl}$ =residual for  $i$  clusters,  $j$  time periods, and  $l$  adolescents.  $Y_{ijl}$  will be modeled for SRH outcomes and interpreted in terms of a contrast of the log odds of response relative to AI youths with similar values for unobserved random effects. In order to test for changes in the tertiary outcomes, we will specify  $Y_{ijl}$  as continuous response outcomes. STATA statistical software will be used to conduct GLMMs. However, SAS will be used if more complex specification of the intraclass correlation becomes necessary.

**3.1.6 Analysis of focus group data.** Focus group data will be transcribed and coded using a partially inductive procedure. First, all transcript data will be open coded (line-by-line coding). The open codes will be pre-sorted based on whether participants are responding to acceptability or fidelity prompts. Within each implementation domain, axial codes will be developed to group the open codes, and the team will meet to discuss how axial codes saturate the pre-defined acceptability and fidelity categories. Transcripts will be coded using Atlas.ti software.

**3.2 Qualitative Data Analysis.** The systems level component and the FAS evaluation component of N/E will be analyzed using content analysis. Common themes will be identified from the two respective sets of data collection instruments. Coding will proceed in stages. A topical indexing scheme will be developed with input from the community advisory board members to identify the text pertaining to particular topics relevant to the systems level and FAS components of N/E. The software program, Atlis.ti will be used to construct and organize a topical indexing system of codes identifying sections of text that capture the central concepts of interests. Then, content coding will be developed by the research team with advice from the community

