**Forms:**

1.) The "Community Advisory Board Meeting Form" will be collected once per quarter after each meeting of the CAB. It will document the barriers and facilitators to intervention implementation discussed at CAB meetings, any social, environmental, political, or bureaucratic contextual factors such as the death of an elder or Tribal Council election year, that may have inhibited or facilitated intervention implementation, and any suggestions to mitigate these barriers the CAB discusses. CAB meeting notes will also be taken during each meeting.

2.) The "Whole Team Meeting Form" will document bi-monthly meetings that include [name], [name], [name], [name], the N/E outreach coordinator, the Cultural Mentor outreach coordinator, and [name]. This form will include any barriers and facilitators to intervention implementation discussed, contextual factors (social, environmental, political, or bureaucratic) discussed, suggestions, and who will be responsible for implementing these suggestions.

3.) The "Staff Training Evaluation Log" will be collected yearly and documents who has been trained, what procedures were followed during training, problems encountered during trainings, and any feedback from the trainings.

4.) The "Fidelity Reach Log and Field Notes" form includes documenting the delivery of the intervention and any field observations study staff note. It will document the date of the intervention, the length of time the intervention was delivered, specific modules delivered, and any barriers and facilitators to the delivery of the intervention.

The outreach coordinator will also document any environmental, social, political, or bureaucratic barriers or facilitators and suggested solutions to the intervention delivery. With the exception of names of staff trained, no identifying data will be collected. These files will be kept in a locked file cabinet by [name] at MSU after data collection.

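### Section 3.1.2 presumes NMAR dropout, but no stated analysis uses that assumption, so comparing imputed with nonimputed data cannot show robustness to it

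*Combined protocol and SAP*

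**What the plan says.** Section 3.1.2 (Missing data) links attrition to truancy, "suggesting a missing data mechanism that is not missing at random (NMAR"). In response it defines a dropout variable and writes a logit for dropout on the previous and the current outcome, presuming that the coefficient of the current outcome, theta_3, is not zero. No value or range for theta_3 is given.

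The section then describes multiple imputation. Students are grouped on a propensity score whose covariates are not listed. Those with missing values are matched to those with observed values, and "missing values will be randomly selected with replacement from the random sample of observed values". The sequence runs from the 3-month to the 12-month follow-up.

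One sensitivity analysis is named: "Sensitivity analyses will also be used to assess the robustness of primary results attributable to missing data by examining imputed and nonimputed data". The nonimputed analysis is not defined.

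Section 3.1.5 (Generalized linear mixed-effects models) gives a model with time, intervention, a cluster effect and a residual. The text also allows for covariates and for autocorrelation within individuals. Results are to be "interpreted in terms of a contrast of the log odds of response". The dropout variable does not appear in it. Section 3.1.1 plans for "the expectation of 15% attrition during the study".

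**The concern.** The plan names a specific threat and says it will address it. Nothing stated after the dropout model does so. Drawing observed donors within propensity groups assumes that, given the propensity variables, students who drop out resemble those who stay. That is MAR, not the mechanism the section presumes.

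The sensitivity check does not fill the gap. If the nonimputed analysis is a likelihood-based GLMM that models within-student correlation, both sides of the comparison rest on MAR. If it is an available-case analysis, neither side allows dropout to depend on the unseen outcome. Either way the two results can agree while both are wrong in the same direction. A reader of the trial report could then take agreement as reassurance about NMAR dropout for the primary outcome.

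**Working it through.** **1. The plan's own figure.** Section 3.1.1: 292 × 1.3273 = 387.57, and 387.57 / 0.85 = 455.97, which rounds up to 456. The stated sample size reproduces. I take its 15% as the share missing by 12 months.

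**2. Tracing the NMAR assumption through the text.**
- Dropout model: theta_3 multiplies the current outcome, which is unobserved for exactly the students who drop out. It cannot be estimated or matched on without further assumptions, and none are given.
- Imputation: observed values, with no shift, tilt or theta_3 stated.
- GLMM: no dropout term, joint model or pattern-mixture term.
- Sensitivity check: no departure from MAR stated.

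**3. Simple arithmetic.** For one 12-month proportion, bias ≈ share missing × (comparable observed students' condom use minus dropouts' condom use). With assumed differences:
- 0.15 × 0.10 = 0.015 (0.015 / 0.14 = 11% of the target effect)
- 0.15 × 0.20 = 0.030 (21%)
- 0.15 × 0.30 = 0.045 (32%)

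**4. Simulation of the 12-month change.**
- From the documents: four occasions, 15% attrition, a 0.14 target.
- Assumed: no true change, 50% use, exchangeable latent correlation 0.5, a binary outcome for every student, no schools or steps.
- Method: dropout at 3, 9 and 12 months, with the logit depending on the current outcome (NMAR) or the previous one (MAR). Imputation is a sequential hot deck within groups of all earlier outcomes. There are at least 400,000 students per setting. The likelihood comparator is linear with exchangeable within-student correlation.

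| Dropout | Odds ratio | Bias of imputed change | Gap to available cases | Gap to likelihood model |
|---|---|---|---|---|
| NMAR | 2 | 0.0104 | 0.0044 | 0.0002 |
| NMAR | 3 | 0.0157 | 0.0065 | 0.0001 |
| MAR | 2 | 0.0002 | 0.0091 | 0.0004 |
| MAR | 3 | 0.0000 | 0.0136 | -0.0001 |

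Repeat NMAR simulations gave biases of 0.0103 to 0.0106 at odds ratio 2 and up to 0.0167 at odds ratio 3, hence the range 0.010 to 0.017. That is 0.010 / 0.14 = 7% to 0.017 / 0.14 = 12% of the target. If condom users drop out more, the sign reverses (-0.0104 and -0.0158).

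**5. How far the size moves.**
- Odds ratios from 1.5 to 5 give absolute biases of 0.006 to 0.022.
- Placing all 15% of dropout at a single 12-month occasion (baseline use 0.45, no dependence on the previous outcome) with theta_3 = -0.5, -1, -1.5 and -2 gives 0.016, 0.034, 0.049 and 0.063. The imputed and complete-case results then differ by only 0.002 to 0.005.

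**The case against.** The plan is not careless about missing data. It has multiple imputation and a sensitivity check, and placing the dropout model next to the imputation suggests that a link was intended. The propensity covariates are unlisted, so truancy is not excluded, and a good measure of it in the propensity model could bring dropout closer to MAR. This is fair, but the link is not written down, and theta_3 cannot enter a propensity score as the text stands. Attendance may not be available either. Section 3.1.3 promises a dose "accounting for individual students' attendance and participation", but Section 4.2.1 says the fidelity log records the date, "the length of time the intervention was delivered, specific modules delivered, and any barriers and facilitators to the delivery of the intervention", and the visible pages of the form show no field for individual students. Session attendance is also not the same as school truancy.

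Three stronger readings are tempting, and the documents do not support them.

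- A reader might infer that the imputed-versus-nonimputed gap reveals the mechanism, because the available-case gap is smaller under NMAR than under MAR in the table. That ordering depends on the comparator. With a likelihood model it vanishes, and the plan does not say which nonimputed analysis it means.
- A reader might carry these figures over to the stepped-wedge intervention effect, or expect NMAR dropout to cancel between control and intervention periods. Section 2.3.5 has follow-up surveys "for the students in the cluster once they have begun participation in the intervention", and Section 4.1 describes the same pattern. As written, every imputed value therefore comes after a school has started, and there are no control-period follow-ups for dropout to cancel against. The trial design figure is not available, so this rests on the text.
- A reader might infer that the trial will overstate its effect, or that dropout alone could produce a 0.14 increase. The bias can go either way, and the largest value in any setting above is 0.063.

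**Conclusion.** The concern holds. The plan presumes NMAR dropout but specifies an imputation valid only under MAR, and its single sensitivity check does not vary that assumption. Agreement between imputed and nonimputed results therefore cannot show robustness to the presumed mechanism.

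This conclusion rests on the wording and needs no particular bias. The 0.010 to 0.017 is an illustration on the risk-difference scale. It depends on assumed condom use, correlation, dropout odds ratio and timing, and the documents fix none of these. The alternative settings show that it could be smaller or several times larger, so the bias is established neither as negligible nor as serious. It is not a bias in the planned GLMM log-odds effect. The change is worth making before analysis, because the gap is clear and cheap to close.

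**What to change.** Amend Section 3.1.2 as follows.

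- State what the written dropout model is for.
- Keep the MAR imputation as the base case, and list the propensity variables. Include school and all earlier outcomes, and add student-level attendance only if it is in fact recorded.
- Name the nonimputed analysis.
- Add one pre-specified NMAR sensitivity analysis, run through the planned GLMM: either a two-sided shift of dropouts' imputed condom use, or the written dropout model over a stated range of theta_3. Report the tipping point at which the 12-month conclusion changes.
- Apply the shift to dropouts only, not to students whom Section 5 of the student survey skips past the condom items because they have never had intercourse.

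The documents give no basis for a particular range. One option is to widen the shift in both directions until the conclusion changes, then judge whether a shift of that size is plausible.

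The cost is SAP wording and a few extra analysis runs on data already planned. The team must fix the shift range, or the widening rule, in advance. Adding attendance is cheap only if it is already captured for each student.
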